2. LIST OF ABBREVIATIONS

Abbreviation	Definition
ACE	Angiotensin Converting Enzyme Inhibitors
AIDS	Acquired Immunodeficiency Syndrome
ARB	Angiotensin-Receptor Blockers
CDC	Centers for Disease Control and Prevention
CDM	Charge Description Master
CI	Confidence Interval
CKD	Chronic Kidney Disease
CNS	Central Nervous System
COVID-19	Coronavirus Disease 2019
CPT-4	Current Procedural Terminology, 4th Edition
ECMO	Extracorporeal Membrane Oxygenation
ED	Emergency Department
ENCEPP	European Network of Centres for Pharmacoepidemiology and Pharmacovigilance
ESRDEUA	Emergency Use Authorization
FDA	US Food and Drug Administration
GPP	Guidelines for Good Pharmacoepidemiology Practices
HCPCS	Healthcare Common Procedure Coding System
HCRU	Healthcare Resource Utilization
HIPAA	Health Insurance Portability and Accountability Act

PFIZER CONFIDENTIAL

HIV	Human Immunodeficiency Virus
IC	Immunocompromising
ICD	International Classification of Diseases
ICD-10-CM	International Classification of Diseases, 10 th Revision, Clinical Modification
ICD-10-PCS	International Classification of Diseases, 10 th Revision, Procedure Coding System
ICU	Intensive Care Unit
IEC	Independent Ethics Committee
IgA	Immunoglobulin A
IgG	Immunoglobulin G
IM	Immuno-Modulators
IMV	Invasive Mechanical Ventilation
IRB	Institutional Review Board
IS	Immunosuppressive
ISPE	International Society for Pharmacoepidemiology
J&J	Johnson & Johnson
LOS	Length of Stay
mRNA	Messenger Ribonucleic Acid
N	Number
N/A	Not Applicable
NDC	National Drug Code
NEC	Not Elsewhere Classified
NOS	Not Otherwise Specified

PASS	Post-Approval Safety Study
PCS	Procedure Coding System
PCV	Proportion of Subjects with Breakthrough SARS-CoV-2 Infections that are Vaccinated
PV	Proportion of the Population that is Vaccinated
Q1	First Quartile
Q3	Third Quartile
QC	Quality Check
RCT	Randomized Controlled Trial
RTIE	Real-Time Insights and Evidence
SARS-CoV-2	Severe Acute Respiratory Syndrome Coronavirus 2
SD	Standard Deviation
STROBE	Strengthening the Reporting of Observational Studies in Epidemiology
US	United States
VE	Vaccine Effectiveness
Vx	Vaccine
WBCs	White Blood Cells
WHO	World Health Organization

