7. RESEARCH QUESTION AND OBJECTIVES

The overall objective of this study is to evaluate characteristics, vaccine utilization and outcomes among vaccinated subjects with IC conditions. The primary analysis will be conducted on subjects vaccinated with BNT162b2. A variety of subgroup analyses are planned, along with multiple sensitivity analyses that will test how variations in study design affect results.

Primary Objectives:

Aim 1: Describe profiles, vaccine utilization and resource use among subjects with IC conditions vaccinated with BNT162b2

Aim 2: Evaluate incidence rates of breakthrough infections among subjects with IC conditions fully vaccinated with BNT162b2

Aim 3: Evaluate the clinical presentation of vaccine breakthrough cases among subjects with IC conditions, including time to infection and severity of disease (hospitalization, mortality)

Secondary Objectives

Evaluate Aims 1, 2, 3 and HCRU/costs over time and stratified by relevant patient characteristics (eg, age), in specific IC conditions and by vaccination type (eg, any Mrna).

Exploratory Objective

Generate early estimates of the effectiveness of BNT162b2 in preventing COVID-19 infection, stratified by relevant patient characteristics (eg, age), in specific IC conditions.

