8.3. Variables

Table 1. Immunocompromising Conditions definition

Variable	Role	Data source(s)	Operational definition
Immunocompromising Conditions	Cohort Definition	HealthVerity Vaccine Data	
Subjects will be categorized into the following 12 mutually exclusive IC groups based on the algorithm detailed in Figure 1:
 
Symptomatic HIV/AIDS, solid malignancy, bone marrow transplant recipients, organ transplant recipients, rheumatologic or other inflammatory conditions, primary immunodeficiencies, other intrinsic immune conditions, chronic kidney disease or end stage renal disease, hematologic malignancy, immunosuppressive treatment only, antimetabolites only, or >1 IC condition.

PFIZER CONFIDENTIAL

Table 1. Immunocompromising Conditions definition

Variable	Role	Data source(s)	Operational definition
			
Subjects falling into more than one of these categories will be categorized as having >1 IC condition.
 
At a minimum, subjects will be required to have one inpatient claim or two outpatient claims on separate days with the IC condition of interest in the baseline period. In cases when >14 days of treatment are required it will be based on the dispensed day supply or distinct days of treatment in the baseline period.
 
The main diagnosis codes to identify IC conditions are presented in ANNEX 1. LIST OF STAND ALONE DOCUMENTS.

Table 2. Vaccination Status definitions

Variable	Role	Data source(s)	Operational definition
Any vaccination	Cohort Definition	HealthVerity Vaccine Data	
Patients with a claim for any vaccine will be considered vaccinated with any vaccine based on the following codes:
 
Pfizer/BioNTech: 91300, 0001A, 0002A, 59267100001, 59267100002, 59267100003
 
Moderna: 91301, 0011A, 0012A, 80777027310, 80777027399, 80777027315, 80777027398
 
Johnson & Johnson: 91303, 0031A, 59676058005, 59676058015
 
Source: https://www.cdc.gov/vaccines/programs/iis/COVID-19-related-codes.html

Fully Vaccinated	Cohort Definition	HealthVerity Vaccine Data	
Patients will be considered fully vaccinated if they meet any of the following definitions:
 
Two claims for Pfizer/BioNTech vaccine on separate days with >14 days of follow-up after the 2nd vaccination date. No claims for any other vaccines are allowed.

PFIZER CONFIDENTIAL

Table 2. Vaccination Status definitions

Variable	Role	Data source(s)	Operational definition

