Other baseline medication use	Patient Characteristics	HealthVerity Vaccine Data	Medications for pre-existing conditions per the Sentinel COVID-19 Natural History Master Protocol (eg, angiotensin converting enzyme inhibitors (ACE), angiotensin-receptor blockers (ARB)).
Vaccine utilization	Patient Characteristics	HealthVerity Vaccine Data	Patterns of uptake. The proportion of IC and non-IC patients who are partially and fully vaccinated with BNT162b2 (or any other vaccines), at different calendar months and follow-up periods (eg, 7 days post dose 2, 14 days post dose 2). Mean, median, minimum, and maximum time between receipt of the first and second dose of BNT162b2 (or any other vaccine)

Table 4. Breakthrough Cases Definition

Variable	Role	Data source(s)	Operational definition
Breakthrough SARS-CoV-2 infection	Outcome	HealthVerity Vaccine Data	Among patients who meet the definition of fully vaccinated, a breakthrough SARS-CoV-2 infection will be defined by evidence of a claim with a diagnosis code of U07.1 that occurs >14 days after the second vaccination date. The first claim with a diagnosis of COVID-19 after this time will be used to assess mean and median time from the second dose until the breakthrough case

PFIZER CONFIDENTIAL

Table 5. COVID-19 Healthcare resource use and Costs definitions

Variable	Role	Data source(s)	Operational definition
Emergency department (ED) visit	Outcome	HealthVerity Vaccine Data	An outpatient claim with a place of service = 23 that occurs after the breakthrough COVID-19 diagnosis date or at the same time/episode of care
Outpatient Hospital Visit	Outcome	HealthVerity Vaccine Data	An outpatient claim with a place of service = 22 or 19 or a standard billing code that begins with '13' that occurs after the breakthrough COVID-19 diagnosis date or at the same time/episode of care
Other Outpatient Visit (not ED, not hospital-based)	Outcome	HealthVerity Vaccine Data	An outpatient claim that does not meet the definition for an ED visit or Outpatient hospital visit.
Hospitalization	Outcome	HealthVerity Vaccine Data	A record from the chargemaster data with encounter type of Inpatient OR a series of claims (separated by no more than 2 days) with a place of service = 21 or standard billing codes that begin with '11' or '12' that occur after the breakthrough COVID-19 diagnosis or at the same time/episode of care 1 st admission and readmissions will be differentiated.

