8.5. Study size

The sample size for this study is fixed by the duration of the observation window. No formal sample size computation will be performed. All subjects who meet the inclusion/exclusion criteria will be included in the analyses.

Feasibility analyses confirmed the availability of data to identify vaccinated subjects, subjects with underlying IC conditions, and breakthrough infections. The current study is mainly descriptive in nature. For the exploratory aim, the entire source population available in the HealthVerity database will be included in the analysis.

[figure not shown]

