8.7. Data analysis

Data analyses will follow extensive feasibility analyses aimed at determining whether a full study and the assessment of vaccine effectiveness are feasible, as illustrated below:

Study implementation approach

Characteristics of the IC, non-IC and total population (IC + non-IC) groups will be described. Descriptive statistics for continuous variables will include N (number of patients), mean, median, standard deviation, Q1, Q3, minimum, and maximum. Categorical variables will be described using frequency counts and percentages.

The incidence rate of breakthrough cases of SARS-CoV-2 infection will be determined based on the following:

- Among fully vaccinated patients, those who have a claim for COVID-19 (ICD-10-CM: U07.1) that occurs on or after >14 days following their second dose of an mRNA vaccine (or 1st dose of Johnson & Johnson) will be considered to have had a breakthrough event. The time from 14 days after the qualifying dose until the breakthrough event will be the person time at risk.

PFIZER CONFIDENTIAL

- Among fully vaccinated patients with no evidence of COVID-19 after their qualifying dose, the time from 14 days after the qualifying dose until the end of follow-up will be the person time at risk.

[figure not shown]
The incidence rate of breakthrough cases of SARS-CoV-2 infection will be calculated as the number of patients who experience the event divided by the observed time at risk, and reported per 100 person years. Poisson 95% confidence intervals will be reported for the incidence rates.

Absolute effect measures such as risk difference between non-IC and IC will be reported. Time period specific effect estimates (eg, at 6 months after vaccination) may be estimated if feasible. The characteristics of the breakthrough infections will be described, including clinical presentation and severity.

The primary analysis will describe results among the non-IC cohort and the IC cohort who are vaccinated with BNT162b2. Subgroup analyses will include results for clinically meaningful subgroups as defined by vaccination type, relevant patient characteristics (eg, age), and each IC condition as listed below:

- HIV/AIDS
- Solid malignancy
- Bone marrow transplant
- Organ transplant (excluding bone marrow)
- Rheumatologic/inflammatory
- Primary Immunodeficiencies
- Other immune condition
- CKD or ESRD
- Hematologic malignancy

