- IS drug use: >14 days IS medications (chemotherapy, immuno-modulators (IM), or corticosteroids excluding low-dose [<60mg/day] prednisone – See Drug List) and not falling into any of the above 9 condition groups
- >14 days of anti-metabolite use and not falling into any of the above 10 condition or drug use groups
- More than 1 IC condition

PFIZER CONFIDENTIAL

Analyses for younger cohorts (eg, 12-15) will also be conducted, as data accumulates.

For the exploratory aim, the Screening Method will be used to calculate VE for the overall study population of subjects with an IC condition and also stratified VE estimates for the different immunocompromised subject groups, with VE also determined for those subjects with >1 IC condition²⁶. We will use the proportion of the population that are vaccinated (PV) and the proportion of subjects with breakthrough SARS-CoV-2 infections that are vaccinated (PCV) to calculate VE using the following formula:

$$VE = (PV - PCV) / [PV(1-PCV)]$$

where PV = the proportion of the population that is vaccinated (ie, vaccination coverage) and PCV = the proportion of subjects with breakthrough SARS-CoV-2 infections that are vaccinated.

Additionally, breakthrough incidence rates and VE will be stratified by age at diagnosis (eg, < 65 and \geq 65 years of age at index vaccination).

Sensitivity analyses will be conducted to test the robustness of findings by varying key study design aspects (eg, continuous enrolment, IC case definition) and data analysis techniques. Other statistical techniques (eg, matched analyses, multiple regression, propensity scores) may be applied on an exploratory basis after careful examination of potential confounders (eg, age, time from vaccination). Exploratory analyses related to alternate dosing may also be conducted upon feasibility results, and as recommendations from public health authorities evolve. The analyses (entirely or in part) will be conducted over time and updated on a rolling basis as monthly data cuts become available.

While the analyses will be focused on the IC population, analyses will also be conducted (in part or entirely) on the non-IC population, the total (IC + non-IC) population or relevant subgroups (eg, other high-risk conditions, vaccination status) to support the interpretation of findings.

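### As worded, PCV in the exploratory screening-method VE equals 1, so VE is undefined; PV also has no reference period although coverage rises from near zero over the window

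*Combined protocol and SAP*

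**What the plan says.** The exploratory objective in section 7 is to "Generate early estimates of the effectiveness of BNT162b2 in preventing COVID-19 infection", by patient characteristics and by IC condition. Section 8.7 assigns this to the screening method, VE = (PV - PCV) / [PV(1-PCV)]. PV is described only as vaccination coverage in the population. For the other term, "PCV = the proportion of subjects with breakthrough SARS-CoV-2 infections that are vaccinated". The abbreviation list in section 2 says the same: "Proportion of Subjects with Breakthrough SARS-CoV-2 Infections that are Vaccinated".

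Breakthrough infection is a defined term. Table 4 in section 8.3 reads: "Among patients who meet the definition of fully vaccinated, a breakthrough SARS-CoV-2 infection will be defined by evidence of a claim" coded U07.1 more than 14 days after the second dose. The incidence-rate definition in section 8.7 starts the same way: "Among fully vaccinated patients, those who have a claim for COVID-19 (ICD-10-CM: U07.1) that occurs on or after >14 days following" the qualifying dose.

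Section 8.5 says that for this aim "the entire source population available in the HealthVerity database will be included in the analysis". Table 2 has separate definitions for any, full and partial vaccination and covers three manufacturers. Table 3 plans uptake by calendar month as a descriptive variable. Index date, baseline, enrolment, the prior-infection exclusion and IC status (sections 8.1 to 8.2.1) all hang on the first vaccine record.

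**The concern.** The screening method compares the vaccinated share of cases with the vaccinated share of the population that produced them. The cases must therefore include unvaccinated people. The plan builds PCV on a case set that its own definitions restrict to the fully vaccinated, so the comparison disappears. This is the only VE estimator the plan specifies; the regression, matching and propensity methods in section 8.7 are optional and undescribed.

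Once the case set is corrected, the result still depends on which PV is used. Coverage climbs from near zero during the window, so one pooled PV need not match the coverage at the time the cases arose. Treatment of partially vaccinated people and recipients of other products also changes the estimate. Unvaccinated people have no index date, so the text gives no way to assign their IC group or eligibility, yet VE is planned by IC group. The error is largest when true VE is low or moderate. That range is relevant here, because section 6 reports lower VE in people with IC conditions.

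**Working it through.** The plan states no value for PV, PCV or VE, so there is no figure to reproduce.

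**1. The formula.** (PV - PCV)/[PV(1-PCV)] equals 1 - [PCV/(1-PCV)] × [(1-PV)/PV], the usual screening-method form. The formula is sound.

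**2. PCV as worded.** Table 4 makes every breakthrough case fully vaccinated, so PCV = 1. The denominator is PV × 0 = 0. The numerator is PV - 1, for example -0.7, -0.5 and -0.3 at PV = 0.3, 0.5 and 0.7. VE is undefined, and it diverges as PCV approaches 1: at PV = 0.5, PCV = 0.99 gives VE = -98 (as a proportion) and 0.999 gives -998.

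**3. PV timing, with PCV taken over all cases.** From the documents: the window of 11 December 2020 to 8 July 2021 is 210 days inclusive (section 8.2). Assumed: nobody fully vaccinated for 35 days, then a linear rise to 30, 50 or 70%; incidence falling tenfold, flat, or rising fourfold; constant VE; no confounding.

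One cell in full, with final coverage 0.70 and true VE 50%:
- Time-averaged coverage = 0.70 × (175/210)/2 = 0.2917.
- Flat incidence: PCV = 0.2917 × 0.5 / (0.2917 × 0.5 + 0.7083) = 0.1707. Time-averaged PV gives 1 - (0.1707/0.8293)(0.7083/0.2917) = 50.0%. End-of-window PV gives 1 - (0.1707/0.8293)(0.30/0.70) = 91.2%.
- Falling incidence: PCV = 0.0857, and time-averaged PV gives 77.2%.
- Rising incidence: PCV = 0.2345, and time-averaged PV gives 25.6%.

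Ranges over the nine scenarios (month-matched means a binomial model with logit of monthly PV as offset, 30-day months, 6 of 7 usable):

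| True VE | Time-averaged PV | End-of-window PV | Month-matched PV |
|---|---|---|---|
| 50% | 26 to 77% | 77 to 96% | 49.5 to 51.0% |
| 80% | 70 to 91% | 91 to 98% | 79.8 to 80.4% |
| 90% | 85 to 95% | 95 to 99% | 89.9 to 90.2% |

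The pooled error at true 90% is therefore about -5 to +9 points. With flat incidence, time-averaged PV returns the true value in all three coverage scenarios.

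**4. Who counts as unvaccinated, with the same rule in PV and PCV.** Assumed: 30-70% fully vaccinated; 5-15% partially vaccinated, with partial-dose VE equal to or half of full VE; or a BNT162b2 share of 40-60% with equal VE for all products.
- Partially vaccinated counted as unvaccinated: true 50% becomes 33 to 49%. Low end: 0.70 fully, 0.15 partially, partial-dose VE 50%. Relative cases are 0.70 × 0.5 = 0.35 against 0.15 + 0.15 × 0.5 = 0.225, so VE = 1 - (0.35/0.225)(0.30/0.70) = 33.3%.
- Other products counted as unvaccinated: true 50% becomes 29 to 46%. Low end: 0.70 fully, share 0.4. Relative cases are 0.28 × 0.5 = 0.14 against 0.30 + 0.42 × 0.5 = 0.51, so VE = 1 - (0.14/0.51)(0.72/0.28) = 29.4%.
- Removing either group from both PV and PCV returns 50%. That holds by construction in this confounding-free illustration.

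**The case against.** The strongest reply is that nobody would carry out the literal reading. The method is named, its formula is right, and section 8.5 brings in the whole source population. An analyst who found PCV = 1 would see the failure at once, so no false VE would be published from it. That stands, and it makes the first part a wording correction. It does not remove the contradiction: the wording recurs in section 2, the term is formally defined in Table 4, and no visible text corrects it.

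On PV, the coverage and incidence curves are outside assumptions, no section selects end-of-window PV, and Table 3 already plans monthly coverage. All true; but nothing links that monthly coverage to PV.

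Two stronger readings are tempting. A reader might infer that the plan pairs one vaccination rule in PV with another in PCV, which could produce extreme, even negative, estimates. The documents do not support this: section 8.7 uses the same word for both terms, and section 7 names the product. A reader might also infer that the PV rule will be picked after the data are seen. The implementation figure announced in section 8.7 is not visible in the text reviewed and may settle PV timing, so that cannot be asserted. It would not cure the PCV wording.

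The sentence in section 8.7 that mixes age at diagnosis with age at index vaccination is minor: over about seven months it moves only people near 65.

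**Conclusion.** The PCV definition is wrong as written: with the plan's own definition of breakthrough infection, VE cannot be calculated. This follows from the text alone. It is probably a drafting slip, and it does not mean that the formula or the method is wrong.

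The PV point is secondary and conditional. A single pooled PV can bias VE when incidence changes over the window. The bias is large at a true VE of 50% and much smaller at 90%. These sizes rest on assumed coverage and incidence curves, and time-averaged PV is unbiased if incidence is flat. Counting partially vaccinated people or other-product recipients as unvaccinated pulls VE down by a moderate amount, under assumed shares.

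The matter should be fixed before VE is estimated. Aims 1 to 3, including the breakthrough incidence rates, are not affected.

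**What to change.** - Redefine PCV in section 8.7 as the proportion fully vaccinated with BNT162b2 (more than 14 days after dose 2, status on the U07.1 date) among all eligible U07.1 cases, vaccinated and unvaccinated, in the same source population that gives PV. Correct section 2 to match.
- Take PV from the monthly coverage planned in Table 3, extended to the source population and matched to each case's calendar month. Match on IC group and age band where counts allow, merging sparse cells.
- State one vaccinated-versus-unvaccinated contrast and use it in both PV and PCV, including where partially vaccinated people and recipients of other products go. Removing them from both is one option.
- Assess IC status and eligibility at a calendar anchor that also exists for unvaccinated people, such as the first day of each month, and state one age definition.

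The PCV correction costs only wording. The rest needs more programming on data already held, gives wider intervals in small IC groups, and loses the earliest cases, when coverage is zero (1 of 7 thirty-day months in the illustration). Removing partially vaccinated people or other-product recipients would also reduce the number of usable cases.

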8.8. Quality control

Data in HealthVerity's COVID Healthcare database are collected weekly in an electronic format. HealthVerity employs its foundational product to match patients between different data sources with high accuracy. However, not all data points are available in every data source and as a result, not all variables in the database are completely populated. In addition, the database contains both pre- and post-adjudicated claims and, based on the data source, adjudication may or may not be captured. To maximize data completeness and uniformity, it may be necessary to exclude certain data sources from the analysis due to differences in data structure and content.

8.9. Limitations of the research methods

There are several limitations associated with this study. The healthcare claims data are

collected for billing purposes and may be subject to misclassification, misdiagnosis, and underreporting. While the sensitivity and specificity of the Greenberg algorithm were 87.4% (95% confidence interval (CI), 80.6-92.5%) and 97.6% (95% CI, 95.0-99.9%), we cannot assess the impact that our modifications had on the accuracy of the algorithm to identify immunocompromised patients. While we used the same codes as Patel²⁵ for HIV, which included HIV only when symptomatic, we cannot be certain about the degree of immunosuppression among patients who had International Classification of Diseases (ICD) codes for symptomatic HIV/AIDS. Further research leveraging Electronic Health Records/ Lab data is warranted to increase sensitivity of capturing symptomatic HIV cases. Due to irregular capture of COVID-19 vaccinations by insurers these results may only be generalizable to a subset of insured individuals. The HealthVerity Census algorithm which links unique patients across disparate data sources may incorrectly assign the same unique identifier to different people or different identifiers to the same person, though this is expected to have negligible impact on the interpretation of results. Additionally, due to the fact that the HealthVerity Data set is comprised of multiple data sources, there may be different levels of missingness for certain variables captured in this analysis.

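### Irregular capture of vaccinations is treated only as a limit on generalizability, but it biases the screening-method vaccine effectiveness itself and can distort the IC versus non-IC contrast in either direction

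*Combined protocol and SAP*

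**What the plan says.** - Section 8.9 acknowledges the data problem and gives one consequence: "Due to irregular capture of COVID-19 vaccinations by insurers these results may only be generalizable to a subset of insured individuals". The same section carries a general caution that billing data can be misclassified or under-reported. It does not link that caution to vaccination status or VE.
- Section 8.3, Table 2 assigns vaccination from claim codes: "Patients with a claim for any vaccine will be considered vaccinated with any vaccine based on the following codes". Full BNT162b2 vaccination requires "Two claims for Pfizer/BioNTech vaccine on separate days with >14 days of follow-up after the 2nd vaccination date", so both doses must have been captured.
- Section 8.7 estimates VE by the screening method from two proportions. PV is the vaccination coverage of the population; for the other, "PCV = the proportion of subjects with breakthrough SARS-CoV-2 infections that are vaccinated". The source of PV is not named.
- Section 8.5 says that for the exploratory aim "the entire source population available in the HealthVerity database will be included in the analysis". This implies, without saying so, that PV is computed in the database.
- The sensitivity analyses in Section 8.7 are open-ended. Their named examples are continuous enrolment and the IC case definition, not vaccination capture.

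**The concern.** A generalizability limit means that the estimate is right for the people studied but may not carry over to others. Missed vaccinations do something different here. A vaccinated person whose doses left no claim cannot be counted as vaccinated, in either PV or PCV. The two proportions do not shrink in a way that cancels in the formula, so the result is wrong for the studied population too, even when capture is the same in cases and non-cases.

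Section 6 gives the purpose of the work as learning which IC conditions predispose to reduced VE, and Section 8.7 plans VE by IC group and by age. Capture may differ by payer, age or condition. An artefact of several points in one stratum could then be read as a biological difference, and no planned analysis would show it.

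**Working it through.** The documents state no VE, coverage or capture value, so there is no planned figure to reproduce. All numerical inputs below are assumptions.

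**Inputs**
- Estimator (Section 8.7): VE = (PV − PCV) / [PV(1 − PCV)], which equals 1 − odds(PCV)/odds(PV).
- True coverage p: assumed 0.6, range 0.5 to 0.7.
- Capture fraction s (share of vaccinated people recorded as vaccinated): assumed 0.5, range 0.5 to 0.9. Nobody is falsely recorded as vaccinated.
- PCV is read as the vaccinated share of all cases.

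**Step 1: no bias with full capture.** True PCV = p(1 − VE) / [p(1 − VE) + 1 − p]. For p = 0.6 and VE = 90%, PCV = 0.06/0.46 = 0.130. The formula gives (0.600 − 0.130)/(0.600 × 0.870) = 0.90, as it should.

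**Step 2: equal capture in cases and population.** The observed values are PV' = sp and PCV' = s × PCV. Substituting gives

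VE' = VE × (1 − p) / [(1 − p) + p(1 − s)(1 − VE)].

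The multiplier is below 1 whenever s < 1 and 0 < VE < 1, so the bias is downward. At p = 0.6, s = 0.5 (PV' = 0.300):

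| True VE | PCV | PCV' | VE' | Points lost | Share of VE lost |
|---|---|---|---|---|---|
| 90% | 0.130 | 0.065 | 83.7% | 6.3 | 7% |
| 70% | 0.310 | 0.155 | 57.1% | 12.9 | 18% |
| 60% | 0.375 | 0.188 | 46.2% | 13.8 | 23% |
| 30% | 0.512 | 0.256 | 19.7% | 10.3 | 34% |

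Over p 0.5 to 0.7 and s 0.5 to 0.9, 90% reads 80.6% to 89.1%, 70% reads 51.9% to 68.0%, and 60% reads 40.9% to 57.7%.

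The proportional loss grows steadily as VE falls. The loss in percentage points does not: it peaks at a true VE of about 51% to 66% (p 0.3 to 0.8, s 0.3 to 0.9) and then shrinks.

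**Step 3: the IC contrast, same p and s in both groups (0.6 and 0.5).**
- True 90% versus 70% (20 points): 83.7 − 57.1 = 26.6 points. Range over the grid in step 2: 21.1 to 28.7.
- True 60% versus 30% (30 points): 46.2 − 19.7 = 26.5 points. Range: 24.4 to 29.7.

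The first gap widens and the second narrows.

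**Step 4: capture or coverage differing between groups (true 90% non-IC, 70% IC, 20 points).**
- p = 0.6, capture 0.5 in non-IC and 0.9 in IC: 83.7 − 67.0 = 16.7 points.
- p = 0.6, capture 0.8 in non-IC and 0.5 in IC: 30.2 points.
- Capture 0.5 in both, coverage 0.8 in non-IC and 0.5 in IC: 75.0 − 60.9 = 14.1 points.

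**Step 5: conditions that turn the bias upward (p = 0.6).**
- Capture 0.5 in the population but 0.3 in cases: 90% reads 90.5%, 70% reads 76.0%, 60% reads 70.4%. The sign changes at a case capture of 0.315 (true 90%) or 0.367 (true 70%).
- Complete external PV of 0.6 with capture 0.5 in cases: 90% reads (0.600 − 0.065)/(0.600 × 0.935) = 95.3%, and 70% reads 87.8%.

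**Step 6: the correction works when s is known.** Dividing PV' and PCV' by their capture fractions restores the inputs: 0.300/0.5 = 0.600 and 0.065/0.5 = 0.130 return 90%. It fails if s is set below the observed proportion; an observed PV of 0.55 with s = 0.5 would give 1.10.

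**The case against.** The plan is not silent on data quality. Section 8.9 warns of misclassification and under-reporting, Section 8.8 lets data sources be dropped for completeness, the sensitivity list in Section 8.7 is open, and VE is conditional on feasibility work. VE is also an exploratory aim described as early estimates, not a formal IC versus non-IC test, and the formula is not used in primary Aims 1 to 3. All of this is true and limits the weight of the point. None of it names vaccination capture, sets a capture criterion for keeping a source, or says how VE would be affected.

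A reader might infer something stronger: that under-capture always lowers VE, lowers a low VE more than a high one, and so exaggerates the IC deficit. The documents do not support that.
- Downward bias needs PV from the same records and capture not materially lower in cases (step 5). Section 8.5 implies the first condition without stating it; nothing addresses the second.
- The larger loss at low VE holds throughout only in proportional terms (step 2).
- A widened IC gap depends on the VE values and on similar coverage and capture in the two groups (steps 3 and 4). The documents report that other studies found lower VE in IC patients, but give no VE for either group.
- Table 2 defines any, full and partial vaccination but never an unvaccinated category. How people with no claim, or with one claim, enter PV and PCV is therefore inferred.

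**Conclusion.** The concern holds in a conditional form. Irregular capture of vaccinations affects the validity of the planned VE as well as its generalizability, and no named analysis examines it. With in-database PV and equal capture in cases and population, the bias is downward, by about 6 points at a true VE of 90% and 13 to 14 points at 60% to 70% under coverage 0.6 and capture 0.5. With capture of 0.9 it falls to about 1 to 3 points at the same coverage (90% reads 88.7%, 60% reads 56.6%).

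No single direction can be claimed for the IC versus non-IC contrast, and the direction of bias in VE itself can reverse. The size rests on assumed coverage, capture and VE, on no false vaccination records, and on one capture fraction for full vaccination status, which ignores recipients with only one dose recorded. The change should be made, but it bears on the exploratory aim only.

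**What to change.** In Section 8.7:
1. State the source of PV, and that it comes from the same records as PCV.
2. Add a bias analysis that recomputes each VE with PV and PCV divided by assumed capture fractions, for example from 0.5 up to 1.0. Limit the fractions to values above the observed PV and PCV. Vary capture separately by IC status and by case status; one common fraction would miss the case-differential scenario that can reverse the sign.
3. Repeat VE in the payers or data sources with the most complete vaccination capture. Payer is already a variable in Table 3.

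In Section 8.9, say that under-capture of vaccinations affects the validity of VE, that the bias is downward if capture is non-differential and PV is in-database, and that the IC versus non-IC contrast can be distorted in either direction.

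The cost is a sensitivity table, one repeated analysis and a revised sentence, with no new data. The drawback is that VE is reported as a range.
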